Despite the high volume of evidence and previous applications of a randomised design, to our knowledge no studies exist that address the delivery and impact of the WRAP intervention with the foster or kinship care community. To our knowledge, the WRAP intervention is not associated with any substantial harms or serious adverse events as a by-product of delivery. However, the following issues were identified in qualitative evaluations of WRAP with adults with mental health difficulties (Canacott, Tickle, & Moghaddam, 2020): not using the plan after WRAP sessions; the plan being an unwelcome reminder of challenging times; the need for follow-up support to revise or support plans; dislike of the group delivery format; and cultural differences in relation to preferences for aspects of WRAP and its delivery.

Logic model

A logic model for the Barnardo's Let's Connect – Fostering Communities (WRAP) programme was developed by Barnardo's, Coram and WWCSC (Figure 1). It sets out the context, intervention, mechanisms and outcomes of the model.

Figure 1. Logic model of the Barnardo's Let's Connect – Fostering Communities (WRAP) model

Evaluation questions

Generic questions	Specific questions	Study
Does the intervention work? ⁴	What impact does referring a family to WRAP, relative to usual support for the mental health and wellbeing of fostering and kinship care families, have on : 1. ... carers' wellbeing ?	Impact evaluation
	2. ... carers' perceived peer support as measured by the number of other foster or kinship carers a carer could ask for help if needed?	Impact evaluation
	3. ...the mental health of children in fostering and kinship households, as reported by their carers?	Impact evaluation
	4. ... carers' family relationships ?	Impact evaluation
	5. ... the rate of placement changes ?	Impact evaluation
Does the intervention work as expected? Does the intervention work differently for some groups? Does the intervention work differently in some places? To what extent was the intervention implemented as intended? What have we learned?	1. To what extent was the intervention implemented as intended compared to the activities detailed in the theory of change and logic model? 2. What is the experience of taking part in WRAP for (birth/foster/kinship) children and their carers? 3. What is the learning from introducing WRAP in the new context of the fostering and kinship community?	Process evaluation Process evaluation Process evaluation

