Total approved fostering households ¹¹	200	105	110	415
Number of foster carers in approved fostering households ⁷	360	175	190	725
Number of looked-after children in foster placements ¹²	661	439	169	1,269

There is no available data on the number of non-foster carer adults or birth children in fostering households. Data leads at the three local authorities informed us that this data is not systematically collected and stored, and is only available through social worker notes. We have assumed one non-foster carer adult per seven fostering households (n=59 other adults), and one birth child per three fostering households (n=138 birth children). The overall pool of fostering households in the three local authorities is therefore 784 adults and 1,407 children.

Following the CONSORT diagram assumptions outlined above, if 95% of all adults and children in intervention trial arm households take part in Level 1 WRAP, this equates to 159 adults and 287 children. As outlined above, kinship carers will be recruited to supplement these numbers and to meet Barnardo's desired delivery of 240 adults and 240 children. We have outlined an approach to mitigate against low uptake rates below.

Inclusion criteria

The trial will include:

- Fostering and kinship households in Hull City Council; North East Lincolnshire Council; and North Lincolnshire Council.
- Fostering and kinship households where at least one adult expresses an interest in taking part in the WRAP programme and its evaluation.
- Fostering households will be prioritised where foster carers are caring for one or more foster children at the time of randomisation.
- Children must be aged nine and over¹³ in order to attend WRAP sessions, but

¹¹ National statistics: Fostering in England 1 April 2021 to 31 March 2022 (2022). Ofsted. www.gov.uk/government/statistics/fostering-in-england-1-april-2021-to-31-march-2022/fostering-in-england-1-april-2021-to-31-march-2022#contacts

¹² National statistics: Children looked after in England including adoptions (2022). Department for Education. <https://explore-education-statistics.service.gov.uk/find-statistics/children-looked-after-in-england-including-adoptions/2022>

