¹³ Barnardo's tell us their experience of delivery of WRAP has largely focused on supporting young people in secondary school, with recent delivery extended to year five and six pupils in Hull. Delivering WRAP to children younger than nine years would require specific permission from the founders and licence holders of WRAP to change aspects of the programme, such as the language used. Barnardo's wants to deliver WRAP to younger children as part of a smaller project before including it in an RCT.

families with younger children can still be randomised (the adult(s) can attend WRAP).

Exclusion criteria

Local authorities will first exclude ineligible families, who:

- Plan to cease fostering in the next year
- Contain at least one child referred for crisis care from CAMHS (urgent or emergency)
- Foster families in crisis and on the verge of placement breakdown

Based on local statistics published by Ofsted we estimate the first criterion would exclude around 25% of families if local authorities had perfect information, but will be approximately replaced by families which start fostering over the same time period. Based on NHS Digital, ONS and DfE data, we assume 19 families will be ineligible due to crisis referrals.¹⁴ Based on March 2021 local Ofsted data, we can expect 1.7 foster carers per foster family and 1.88 foster children per foster family.

Procedures

Local authorities will provide carer contact information to Barnardo's, and Barnardo's will send eligible families an invitation to an information session. Barnardo's will facilitate information sessions, with the aim of giving prospective participants clear information about the programme and evaluation to inform their decision whether to express interest. Delivery of information sessions will be ongoing throughout the programme, and a minimum delivery of two per week is anticipated, with more at certain points e.g. in the start-up period. They will include co-delivery with some fostering and kinship community members after their completion of WRAP Level 1 groups.

After attending an information session, interested participants will complete an Expression of Interest form. Barnardo's will collate these and send the details of these households to Coram for randomisation. We will randomise the stock of families in February 2023, and then on demand as needed for the in-flow of newly eligible families thereafter until early 2024.

Mitigations in case of low uptake

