We will request administrative data from local authorities in March 2024. We will follow DfE SSDA903 requirements to the greatest extent possible, to minimise burden. Some data will have the foster child as the unit of analysis, and some will have the carer as the unit of analysis. We will use an Excel template for the data request that will be partially completed with demographic information about carers and children provided at randomisation. This entails routinely collected data on the care status and living arrangements of children, numbers and dates of placement changes, foster carer turnover management information (unique ID of the foster carer and step-down dates), and Strengths and Difficulties Questionnaire (SDQ) total difficulties scores for foster children (and date of the score and the unique ID of the child). We will gather SDQ scores from local authorities in March 2024, which according to published figures should be available for around 84% of looked-after children. A full breakdown of variables is provided in the spreadsheet template in Appendix 2.

For our secondary outcome of **placement changes**, we will seek data on the following variables for each foster child:

1. Number of placements since randomisation

¹⁷ Collins, J., Gibson, A., Parkin, S., Parkinson, R., Shave, D., & Dyer, C. (2012). Counselling in the workplace: How time-limited counselling can effect change in well-being. *Counselling and Psychotherapy Research*, 12(2), 84-92.

¹⁸ Maheswaran, H., Weich, S., Powell, J., & Stewart-Brown, S. (2012). Evaluating the responsiveness of the Warwick Edinburgh Mental Well-Being Scale (WEMWBS): Group and individual level analysis. *Health and Quality of Life Outcomes*, 10(1), 1-8.

¹⁹ Hamilton, E., Carr, A., Cahill, P., Cassells, C., & Hartnett, D. (2015). Psychometric properties and responsiveness to change of 15- and 28-item versions of the SCORE: A family assessment questionnaire. *Family process*, 54(3), 454-463.

2. Date of first placement change since randomisation (if applicable)
3. Nature of second placement (if applicable)
4. Reason for first placement change (if applicable)
5. Other reason for first placement change (if applicable)
6. Date of second placement change since randomisation (if applicable)
7. Nature of third placement (if applicable)
8. Reason for second placement change (if applicable)
9. Other reason for second placement change (if applicable)
10. Date of third placement change since randomisation (if applicable)

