- dummy variable for gender of foster carer or kinship carer (female, male, neither, unknown);
- dummy variables for ethnic group of foster carer or kinship carer (Asian, Black, Mixed, Other, White, unknown);
- dummy variable for age of foster carer or kinship carer (21-24, 25-34, 35-44, 45-54, 55-64, 65-74, 75-84, 85 and over, unknown);
- dummy variable for whether a single carer or couple (single, partner, unknown);
- deprivation indicator (derived from postcode district);
- baseline WEMWBS score;
- time from randomisation (in months).

If any of the cells defined as above have fewer than 10% of cases, we will merge them with another cell.

We may also include time from first session of intervention in our analysis to explore whether the time between participation and survey completion is associated with outcomes.

Secondary outcomes analysis

Regression models will be used to analyse secondary outcomes. For the majority of outcomes, these will also be linear regression models. We will also run a Poisson regression, and zero-inflated Poisson regression as sensitivity tests in the event that the data contains a substantial number of zeroes. Our approach to reporting on baseline characteristics and adjusting for missing data will be the same as those outlined above. The models used for each secondary outcome are outlined below:

- Carers' perceived peer support: Linear regression (with zero-inflated Poisson regression)
- Mental health of children in household: Linear regression
- Carers' family relationships: Linear regression

For our placement changes outcome, we will analyse this according to our pre-specified reason categories but for robustness will also explore the impact on point estimates and effect sizes when alternative categories are used. For example, we may run a logistic regression where any placement change is included as a placement change regardless of the reason for the change.

The mental health of children will be analysed separately as measured by the BAC and the SDQ. As the SDQ is only available for foster children, this sample size will be smaller i.e. no kinship or birth children. Following What Works for Children's Social Care statistical analysis guidance, our secondary outcomes will be adjusted for multiple tests using the Hochberg's step-up procedure for all secondary analyses.

Other evaluation questions

Exploratory analysis

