We will also look at attendance as a proportion of household members (e.g., two out of four household members attending means 0.5 attendance) as an instrumental variable in outcomes, as well as the attendance of children at WRAP sessions in relation to their scores on the SDQ and BAC. We may conduct an exploratory dosage analysis with the number of sessions as the instrumental variable, as opposed to binary non-/attendance.

Analysis of harms

We will analyse the proportion of foster children that demonstrate reliable and clinically significant deterioration between their 'pre' and 'post' SDQ scores. For a clinically significant deterioration we will report the proportion of foster children that move from a pre score of below 17 to above at post-test i.e. the clinical threshold for the SDQ (Goodman, 2001²²; Goodman, Ford, Simmons *et al.*, 2000²³). For reliable deterioration, we will report the proportion of foster children that show an increase in SDQ score from pre to post test that is greater than the reliable change index (Jacobson and Truax, 1991²⁴).

Process evaluation

Evaluation questions

²² Goodman, R. (2001). Psychometric properties of the strengths and difficulties questionnaire. *Journal of the American Academy of Child and Adolescent Psychiatry*, 40(11), pp.1337-1345.

²³ Goodman, R., Ford, T., Simmons, H., Gatward, R., & Meltzer, H. (2000). Using the Strengths and Difficulties Questionnaire (SDQ) to screen for child psychiatric disorders in a community sample. *British Journal of Psychiatry*, 177, pp.534-539.

²⁴ Jacobson, N. S., & Truax, P. (1991). Clinical significance: a statistical approach to defining meaningful change in psychotherapy research. *Journal of Consulting and Clinical Psychology*, 59(1), pp.12-19.

The process evaluation consists of three summative questions under three themes: delivery of the intervention; participant experiences and learning for future delivery:

Delivery of the intervention

- A. To what extent was the intervention implemented as intended compared to the activities detailed in the theory of change and logic model?
- This will consider:
 - What are the core elements of the intervention that was delivered?
 - How does the delivered intervention vary across groups?
 - How is it different to usual support provided to the foster and kinship community?
 - What are the barriers and enablers to successful implementation of WRAP?

Participant experiences

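### The harms analysis defines individual deterioration only on the SDQ and only in foster children, leaving out carers, birth children and kinship children who also receive WRAP

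*Protocol*

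**What the plan says.** The Analysis of harms section of the protocol sets two measures. For clinically significant deterioration, "we will report the proportion of foster children that move from a pre score of below 17 to above at post-test". For reliable deterioration, "we will report the proportion of foster children that show an increase in SDQ score from pre to post test" by more than the reliable change index. Neither has an age or attendance restriction, and no other scale or group is named.

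The Secondary outcomes analysis section confirms who this covers: "As the SDQ is only available for foster children, this sample size will be smaller i.e. no kinship or birth children". The Outcome measures section expects that SDQ scores "should be available for around 84% of looked-after children".

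The Level 1 WRAP delivery section lists the recipients as foster, kinship and birth children, foster and kinship carers, other adults in the household, and social workers (who are not randomised). Delivery starts with adults. The Evidence base section reports unwelcome experiences from qualitative studies of adults with mental health difficulties, among them "the plan being an unwelcome reminder of challenging times".

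The Outcome measures section collects carer WEMWBS at both waves, and a BAC-C or BAC-A, by child age, for every household child aged four and above. The Avoiding harm section adds regular communication with the delivery organisation and the local authorities about emerging harms, without a measure, threshold or analysis.

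**The concern.** The harms section follows the data source (the SDQ from local authority returns) and not the people who receive the programme. Adults are the first group to receive WRAP and the group in which the protocol itself records negative experiences, yet no count of adults who deteriorate is planned. The same holds for birth and kinship children.

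A mean comparison does not replace such a count. If a fraction q worsens by d while the rest improve by e, the mean change is (1 − q)e − qd, which can be zero or favourable while q is not negligible. The protocol accepts this reasoning for foster children, since it compares SDQ means and also counts deteriorations.

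At stake is the reach of the trial's conclusion on harm. Followed as written, a finding of little deterioration would rest on foster children alone, and a reader could take it to apply to everyone who attended.

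**Working it through.** **1. Reproduce the protocol's expected attendance.** The summary table gives 311 foster carers, 25 other adults, 544 foster children and 59 birth children to be randomised 50:50. The Participants section applies 95% participation and says "this equates to 159 adults and 287 children".

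- Adults: 0.95 × (311 + 25) / 2 = 159.6 (stated 159).
- Children: 0.95 × (544 + 59) / 2 = 286.4 (stated 287).

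Both agree to within rounding.

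**2. Split by coverage of the harms section.**

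| Group, intervention arm | Calculation | Expected | In harm analysis? |
|---|---|---|---|
| Foster carers | 0.95 × 311 / 2 | 147.7 | No |
| Other adults | 0.95 × 25 / 2 | 11.9 | No |
| Birth children | 0.95 × 59 / 2 | 28.0 | No |
| Foster children | 0.95 × 544 / 2 | 258.4 | Yes, if SDQ available |
| Kinship adults and children | not given | unknown | Kinship adults and kinship children: no |

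About 160 adults and 28 birth children are therefore outside it, before kinship members.

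**3. Is there a score that could be used?**

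- Carers: WEMWBS at baseline and endline. Yes.
- Birth and kinship children aged four and above: carer-reported BAC at both waves. Yes.
- Other adults: unclear. The Outcome measures section sends the survey to carers, while the sample size section counts other adults among the survey responses.

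**4. Do other provisions give an individual count?**

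- Two-sided arm comparisons of WEMWBS, BAC and SCORE-15 give means only.
- CAMHS referrals are expected to be available for foster children only.
- The Avoiding harm section would leave out of interview families in crisis and for whom WRAP proved upsetting. It concedes that this tilts the evidence towards good experiences, and relies on professionals for the rest.

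None of these yields a proportion deteriorating among carers, birth children or kinship children.

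**5. Under-nines in the SDQ denominator.** The Inclusion criteria section says "Children must be aged nine and over" to attend sessions, but "families with younger children can still be randomised (the adult(s) can attend WRAP". At 84% availability, 0.84 × 544 = 457 randomised foster children would have an SDQ. The protocol gives no age split. Assuming 10% to 50% are under nine and availability does not vary with age, 46 to 228 of the 457 could not have attended.

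**The case against.** The strongest reply is that these groups are not ignored. Carer WEMWBS is the primary outcome, tested two-tailed. BAC and SCORE-15 are compared by arm, adult and child type may enter exploratory models, and child attendance is examined against BAC and SDQ scores. A worse mean in the WRAP arm would be seen. This stands: the gap is a missing count of individual deterioration, not a failure to look at these groups at all.

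It can also be said that extra harm summaries belong in a statistical analysis plan, which is not shown. That carries less weight here, because the protocol has a dedicated harms section that itself fixes the measures and the population.

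Three stronger readings are tempting, and the documents do not support them.

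- *A reader might infer that including under-nines is an error.* Randomisation is by household, the analysis is by intention to treat, and the adults in these families can attend, so young children may be affected through their carers. Their inclusion can dilute a signal of direct harm, but it is defensible.
- *A reader might infer that the gap weakens the provision for ending the trial early.* That provision rests on communication during the trial. The last delivery phase is April to June 2024 and the endline survey goes out on 1 July 2024, so no pre/post analysis could inform it.
- *A reader might quote the uncovered share of recipients.* Step 2 gives 187.6 / 446.0 = 42%. With the 1.88 foster children per family in the Exclusion criteria section, 0.95 × 89 × 1.88 = 159 foster children, and the share is 187.6 / 346.6 = 54%. Neither is a share of actual attenders, because the child totals include under-nines who cannot attend.

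**Conclusion.** The point holds in this form: individual deterioration is defined only for foster children and only on the SDQ, while carers, birth children and kinship children also receive WRAP and have repeat scores that could be used. On planning numbers this leaves out about 160 intervention-arm adults and 28 birth children, plus an unknown number of kinship members.

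The adult figure rests on the protocol's assumed 95% participation and includes about 12 other adults whose survey coverage is unclear. The birth-child figure rests on the protocol's assumption of one birth child per three households and does not remove under-nines. The protocol's statements are not false. The fault is a harms section narrower than the group exposed, and it is worth correcting because the data are already planned.

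**What to change.** In the Analysis of harms section, add by randomised arm, as descriptive estimates:

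- the proportion with reliable deterioration on WEMWBS (a fall), in all surveyed adults with both waves, stating whether other adults are surveyed;
- the proportion with reliable deterioration on BAC (a rise), in all children with the same BAC form at both waves, shown separately for foster, kinship and birth children.

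Use the reliable-change method already planned for the SDQ, and state the reliability value for each scale, either published or estimated in the sample. Optionally, show the child results for those aged nine and over at randomisation alongside all children. Word any conclusion on harm so that it names the groups assessed.

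**Cost.** No added burden on participants, but more than a trivial addition to the analysis:

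- The protocol gives no reliability values for WEMWBS or BAC.
- Some children will move from BAC-C to BAC-A between waves, which are about 16 months apart for families entering in March 2023, and drop out of the same-form analysis.
- BAC was developed for looked-after children, and the protocol expects other children may score differently.
- BAC is reported for children currently in the household, so those who left will lack an endline score.
- Adult numbers are limited by response: the protocol expects 234 analysable adults in fostering households over both arms, and fewer if baselines are missing.
- Estimates for birth and kinship children will be imprecise.

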Annex 1: CONSORT diagram with numbers of kinship carers²⁷

²⁷Numbers taken from Kinship's constituency estimates at [Constituency map \(kinship.org.uk\)](http://Constituency map (kinship.org.uk)) accessed 10/02/23

Annex 2: Code used to calculate Minimum Detectable Effect Size

```
install.packages("PowerUpR")
library("PowerUpR")

#Primary outcome: Foster carer perceived peer support
#Two-Level Blocked (Fixed) Cluster-level Random Assignment Design
#Level 2 = Family, Level 1 = Adult
#Treatment and randomisation at Level 2

mdes.bcra3f2(power=.80, alpha=.05, two.tailed=TRUE,
             rho2=.4, p=.50, g2=0, r21=0.6, r22=0,
             n=1.9, J=41.3, K=3)
```

